7.5 Subject Discontinuation/Withdrawal from the Study

Subjects may be discontinued/withdrawn from the study for reasons that include, but are not limited to, the following:

- A subject may withdraw from the study at any time at his/her own request, or he/she may be withdrawn at any time at the discretion of the Investigator for safety, behavioral, compliance, or administrative reasons.
- If the subject withdraws consent for disclosure of future information, the Sponsor may retain and continue to use any data collected before such a withdrawal of consent.
- If a subject withdraws from the study, he/she may request destruction of any samples taken and not tested, and the Investigator must document this in the study center study records.
- See [Section 1.2](#) for the data to be collected at the time of study discontinuation and follow-up and for any further evaluations that need to be completed.

The discontinuation of specific study centers or of the study are handled as part of [Appendix 2](#).

7.6 Lost to Follow-Up

A subject will be considered lost to follow-up if he or she repeatedly fails to return for scheduled visits and the study center is unable to contact him/her as described below.

The following actions must be taken if a subject fails to return to the clinic for a required study visit:

- The study center must attempt to contact the subject and reschedule the missed visit as soon as possible and counsel the subject on the importance of maintaining the assigned visit schedule and ascertain whether the subject wishes to and/or should continue in the study.
- Before a subject is deemed lost to follow-up, the Investigator or designee must make every effort to regain contact with the subject (where possible, 3 telephone calls and, if necessary, a certified letter to the subject's last known mailing address or local equivalent methods). These contact attempts should be documented in the subject's medical record.
- If the subject continues to be unreachable, he/she will be considered to have withdrawn from the study and lost to follow-up.

8.0 STUDY ASSESSMENTS AND PROCEDURES

Study procedures and their timing are summarized in the Schedule of Activities ([Section 1.2](#)). Adherence to the study design requirements, including those specified in the Schedule of Activities, is essential and required for study conduct. Procedures conducted as part of the subject's routine clinical management (eg, blood count) and obtained before signing the informed consent form (ICF) may be utilized for Screening or Baseline purposes provided the procedures met the protocol-specified criteria and were performed within the time frame defined in the Schedule of Activities.

All Screening evaluations must be completed and reviewed to confirm that potential subjects meet all eligibility criteria. The Investigator will maintain a screening log to record the details of all subjects screened and to confirm eligibility or record reasons for screening failure, as applicable.

Protocol waivers or exemptions may be permitted at the Sponsor's discretion, especially when mitigating factors associated with a global pandemic and other situations that arise that are outside the control of the Sponsor and/or Investigator. Immediate safety concerns should be discussed with the Sponsor immediately upon occurrence or awareness to determine if the subject should continue or discontinue study treatment.

8.1 Study Visits

This study will consist of 6 visits as described in the Schedule of Activities ([Section 1.2](#)). The maximum amount of blood collected from each subject over the duration of the study will be approximately 20 mL. Repeat or unscheduled samples may be taken for safety reasons or for technical issues with the samples.

8.1.1 Visit 1 (Screening)

Screening will occur at Visit 1 (Day -90 to Day -7). Subjects can be screened for the study up to approximately 90 days before Baseline. During Screening, the study requirements and procedures will be reviewed and written informed consent/assent will be obtained prior to the initiation of any study-related procedures. Following informed consent, a review of inclusion exclusion will be conducted so that the Investigator can assess if the subject is likely to be eligible for enrollment. Once this is confirmed, the availability of genetic testing confirming the diagnosis of CI and specific subtype will be addressed. Subjects who already have had genetic test documenting ARCI-LI or RXLI types of CI will not be required to provide samples for genetic testing. However, the subject must provide the Investigator with a copy of the genetic report for the source documentation file. Subjects requiring genetic testing, will have a buccal specimen obtained and sent for analysis. Following confirmation of the appropriate genetic subtype, the following procedures will be completed in the Screening period; Demographics, medical history, concomitant medications, physical exam, vital signs, clinical evaluation of extent and location of CI, percent BSA with CI in the Treatment Area, as well as in the VIIS Assessment Area, and

clinical laboratory test as found in [Table 7](#). In addition, VIIS for scaling will be performed for the VIIS Assessment Area and IGA for Scaling and Fissure will be performed for the Treatment Area.

Subjects who meet all inclusion criteria and no exclusion criteria will be randomized to a treatment group stratified by CI subtype. Randomization will be performed as specified in [Section 6.3](#).

8.1.2 Visit 2 (Baseline)

Baseline activities will occur at Visit 2. This visit may be performed either on site or as a remote, tele-medicine visit.

The following will be conducted at the visit:

- The subject will be queried for any changes in health status (ie, change in medications or new health issues) since the previous visit, including concomitant medications and concurrent procedures/therapies
- Abbreviated physical exam/ subject disposition via directed query
- Eligibility will be confirmed. All WOCBP must have a negative UPT.
- Photography per a photographic guide provided by the Sponsor (at select study sites and for all subjects where this visit will be conducted remotely)
- Clinical evaluations will be performed prior to the application of study medication. Confirmation of the percent BSA with CI in the Treatment Area and the VIIS Assessment Area
- VIIS for Scaling will be performed for the VIIS Assessment Area and IGA for Scaling and Fissure will be performed for the Treatment Area.
- Age-appropriate Dermatology Life Quality Index (DLQI) and Itch-Numeric Rating Scale (I-NRS) will be completed by the subject.
- Study personnel will review and dispense the Subject Instruction Sheet and Diary. The subject and parent/guardian (if applicable) will be instructed on how and where to dispense and apply study medication to the Treatment Area and to record applications in the Subject Diary.
- If the visit is being held in clinic, the tubes with study medication will be weighed by study personnel prior to dispensing to subject. If the visit is being held remotely, the subject will weigh the tubes with study medication prior to using. Subjects will apply the first dose of the assigned study medication to all affected skin in the Treatment Area under staff supervision either in person or remotely.
- All AEs post application will be recorded.

8.1.3 Visit 3, Visit 4, and Visit 5

Visit 3 will take place at Week 2 on Day 15 \pm 4 days; Visit 4 will take place at Week 4 on Day 29 \pm 4 days; and Visit 5 will take place at Week 8 on Day 57 \pm 7 days. These visits may be performed either on site or as a remote tele-medicine visit.

The following will be completed at these visits:

- The subject will be queried for any changes in health status since the previous visit, including concomitant medications and concurrent procedures/therapies. Any AEs will be documented.
- A UPT will be performed for WOCBP at Visit 4 and Visit 5 only. Note: If the UPT result is positive, the subject must discontinue treatment immediately; and the Investigator must report the pregnancy as detailed in [Section 8.4.5](#) and [Appendix 6](#).
- Photography will be performed at select study site(s) per a photo guide provided by the Sponsor and for all subjects where any of these visits will be conducted remotely.
- Clinical evaluations including local skin reactions and determination of the percent BSA with CI in the Treatment/Assessment Areas and overall percent BSA will be performed.
- VIIS for Scaling will be performed for the VIIS Assessment Area and IGA for Scaling and Fissure will be performed for the Treatment Area.
- Age-appropriate DLQI and I-NRS will be completed by the subject at Visit 5 only. Record percent of BSA with CI in the VIIS Assessment Area and the Treatment Area
- Study treatment accountability will be performed, including weighing of all newly dispensed and returned tubes.
- The Subject Diary will be collected, reviewed, and re-dispensed.
- The Subject Instruction Sheet will be re-dispensed as necessary. Subjects will be instructed to continue bid treatment in the morning and evening until the next visit and to record all applications in the Subject Diary.
- The subject will be scheduled for the next visit.

8.1.4 Visit 6 (End of Study)

The EOS visit will occur at Week 12 on Day 85 \pm 7 days. Any subject who is discontinued from study prior to Visit 6 (EOS) should complete the procedures listed for EOS during their last study visit or Early Termination visit. This visit may be performed either on site or as a remote visit, although all efforts should be made for an on-site visit.

The following will be completed at this visit:

- The subject will be queried for any changes in health status since the previous visit, including concomitant medications and concurrent procedures/therapies. Any AEs will be recorded.
- Age-appropriate DLQI and I-NRS will be completed by the subject.

- Abbreviated physical examination/ subject disposition via directed query, vital signs, clinical laboratory tests
- Photography (select study sites and for all subjects where this visit will be conducted remotely)
- UPT for WOCBP will be performed
- The study staff will perform the clinical evaluations , including local skin reactions and record the percent BSA with CI in the Treatment Area and VIIS Assessment Areas
- VIIS for Scaling will be performed for the VIIS Assessment Area and IGA for Scaling and Fissure will be performed for the Treatment Area.
-
- Study treatment accountability will be performed, including weighing of all returned tubes.
- The Subject Diary will be collected and reviewed.

8.2 Efficacy Assessments

At each visit, the skin affected with CI in the Treatment/Assessment Areas defined at the Baseline Visit will be assessed as described below.

8.2.1 Visual Index for Ichthyosis Severity – Scaling

The Investigator will include subjects when any of the 4 VIIS Assessment Areas have some CI disease. At least 2 of the 4 VIIS Assessment Areas MUST have a scaling score of 3 or more. The upper arm, lower leg/shin, and dorsal foot each include left and right body parts. Therefore, one of each left or right must be designated as the Target (upper arm, lower leg, or dorsal foot) and followed throughout the study for VIIS assessment. The arm, leg, or foot with more severe and higher score will be designated as the Target unless they have the same severity scores, in which case the left or right choice will be at the discretion of Investigator assuming no other issues exists, dictating the choice of left/right. The severity scores will be averaged by the electronic data capture system but the score of the two body parts that have a score of 3 or higher will be used to enroll subjects and used in subsequent assessments.

The location of the CI to be treated and the percent body surface area (BSA) with CI in the Treatment Area and in the VIIS Assessment Areas will be recorded prior to application of study medication.

Scaling in the VIIS Assessment Areas will be graded using the 5-point VIIS scale: 0 to 4. This is a visual assessment tool to assist with scoring in 4 specific body sites, so it is essential to include at least 2 or more of the 4 body sites with CI in the Treatment/Assessment Areas. The Assessment Areas are described in [Section 4.1.2.1](#). Visual Index for Ichthyosis Severity “Treatment success” (VIIS-50) is defined as a 50% or greater decrease in VIIS scaling score relative to Baseline at Visit 6 (EOS) calculated using the sum of the scores for ‘VIIS body areas’ that have a Baseline score ≥ 3 .

VIIS severity will be calculated as above using the scores obtained via one of two methods below:

- a) On-site visual inspection of the VIIS areas
- b) Virtual/ Remote visit comprised of both photographs and tele-medicine utilizing synchronous video conferencing technology. The severity score at each visit will be based off information gathered from both sources to yield one score.

8.2.2 Investigator’s Global Assessment

The IGA score is a static evaluation of the overall or “average” degree of severity of a subject’s disease, considering all the subject’s scaling and fissuring in the Treatment Areas by the Investigator or designee. This evaluation takes into consideration the 2 individual characteristics of CI (scaling and fissuring) with the IGA score at each visit representing the average degree of scaling and fissuring that is eligible for treatment. The Treatment Areas are described in [Section 4.1.2.2](#). The IGA will be assessed using the following 5-point scale shown in [Table 3](#):

Table 3 Investigator’s Global Assessment Score (5-Point Scale)

0 =	Clear	No scaling and no roughness, no fissure
1 =	Almost Clear	Occasional fine scales, hardly palpable roughness (mostly smooth) no fissure
2 =	Mild	Small and fine scales predominate, no more than a few large scales, mild roughness on palpation, few fissures may be present
3 =	Moderate	Large rather thick scales predominate, coarse roughness on palpation, few fissures may be present
4 =	Severe	Large coalescent scales dominate, sharp edges on palpation with plate-like hyperkeratosis, many fissures may be present

IGA severity will be calculated as above using the scores obtained via one of the two methods below:

- c) On-site visual inspection
- d) Virtual/remote visit comprised of both photographs and tele-medicine utilizing synchronous videoconferencing technology. The severity score at each visit will be based off information gathered from both sources to yield one score.

8.2.3 Itch-Numeric Rating Scale

Pruritus will be assessed with a self-administered Patient Reported Outcome questionnaire using the I-NRS at Visit 2 (Baseline), Visit 5, and at Visit 6 (EOS). Subjects will indicate itch severity by circling the integer that best describes the worst level of itching due to CI in the past 24 hours on an 11-point scale anchored at 0 representing “no itching” and 10 representing “worst itch imaginable.” (see [Appendix 11](#)). The study staff should review the I-NRS with each subject and

ask him/her to indicate the response that best describes his/her experience. Pruritus assessed by this evaluation should be reported as an AE only if therapy is required.

8.2.4 Percent Body Surface Area with Active Congenital Ichthyosis in the Treatment/Assessment Areas

The percent BSA with active CI within the Treatment Area will be calculated at Visit 1 (Screening). The Treatment Area includes all affected skin **excluding** the hands, face, neck, scalp and genitalia. This calculation is confirmed at Visit 2 (Baseline) and assessed at all follow-up visits. The minimum affected area to be treated will be no less than 10% and no more than 90% of the whole BSA at Visit 1 (Screening). In addition, the percent BSA with active CI within the designated VIIS /Assessment Areas will be calculated at Visit 1 (Screening) and at all follow-up visits. Note that the Treatment Area is at least equal to or larger than the VIIS Assessment Area. Based on the Treatment and VIIS Assessment Areas selected in a given subject and the extent of his/her disease, these two areas may or may not be the same. Two examples are provided below for clarity:

	Treatment Area % BSA	VIIS Assessment area % BSA
Subject 1	90% (entire body minus hands, face, neck, scalp, genitalia)	24% (upper back, upper arms, lower legs and dorsal feet)
Subject 2	70%	13% (upper back and upper arms)

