2.3 Benefit/Risk Assessment

While no topical isotretinoin formulation is approved for use in treatment of CI (or any indication in the US), topical formulations of isotretinoin (eg, 0.05% gel and 0.1% cream) have demonstrated some efficacy in reducing the clinical signs associated with ichthyosis and other disorders of keratinization. In one study, topical 13-cis-RA (isotretinoin) cream 0.1% demonstrated a marked reduction in scaling and an improvement in skin smoothness after 4 weeks of treatment in 40% of subjects (2/7 patients with non-erythrodermic LI, 2/2 patients with Darier's disease, and 0/1 patients with autosomal dominant ichthyosis vulgaris). However, this clinical improvement was accompanied by local skin irritation (eg, itchy erythema) in responders, and dose modifications were often prescribed to mitigate such effects (12). Similarly, topical isotretinoin gel, 0.05% (Isotrex®) demonstrated partial resolution or clearance of hyperkeratosis and papules in the treatment area (10 cm² area) after 3 months of treatment (up to twice daily [bid] as tolerated) in 50% (6/12) of patients with Darier's disease.

In addition, systemic retinoids, including isotretinoin, have been used for the investigational treatment of CI and have demonstrated remarkable efficacy in reducing the clinical signs of the disease while dosing of the drug is maintained (1, 5).

More recently, a pilot Phase 2a, multicenter study in subjects ≥ 12 years of age showed topically applied TMB-001 ointment (0.1%) to be safe, tolerable, and supporting a favorable efficacy signal with improvement in overall IGA for CI treatment.

As with any retinoid, the side effects of TMB-001 may include the following local skin reactions (LSRs): burning, dryness, edema, erythema, hyperpigmentation, hypopigmentation, photosensitivity, pruritus, scaling/peeling, stinging, and tenderness.

Although systemic exposure is expected to be low given the route of topical administration. In minipigs receiving once daily dermal applications of TMB 001 ointment at concentrations of 0% (control), 0.025%, 0.1%, and 0.2%, there was little to no systemic absorption of isotretinoin with most values being near or below the limit of quantitation (0.374 ng/mL).

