8.3.3 Local Skin Reactions

At every study visit (except Screening), the Investigator or designee will evaluate LSRs known to be associated with retinoids (burning/stinging, erythema, erosions, and edema) or other causes regardless of blinded causality assessment within the areas treated with study medication using a 4-point ordinal scale where 0 = none, 1 = mild, 2 = moderate, and 3 = severe. Note: At Visit 2 (Baseline), the LSR assessment must be performed prior to the application of study medication. Only LSRs that require medical intervention (eg, prescription medication) or that require withholding application of the study medication will be documented as AEs. Any LSRs that are not listed above will be recorded as AEs. For drug interruption due to LSRs, refer structured drug interruption scheme (drug holiday) described in [Section 7.4](#).

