8.4.6 Adverse Events of Special Interest

No events will be considered as AEs of special interest for this study.

8.4.7 Disease-Related Events and/or Disease-Related Outcomes Not Qualifying as Adverse Events or Serious Adverse Events

Disease attributes that are associated with underlying disease condition should not be reported as AEs. Local skin reactions associated with retinoids should not be reported as AEs unless the LSRs required medical intervention or withholding application of study medication (refer [Section 8.3.3](#) for complete details).

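### Protocol 8.2.3 conflicts with 8.3.3 on when pruritus is an adverse event and omits withholding as a trigger, and no graded itch score is scheduled at Weeks 2 and 4

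*Protocol*

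**What the plan says.** Three sections of the protocol bear on whether itch is an adverse event.

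- Section 8.2.3 (I-NRS): pruritus found with this scale "should be reported as an AE only if therapy is required". Withholding of study medication is not mentioned.
- Section 8.3.3 (LSRs): the investigator scores "LSRs known to be associated with retinoids (burning/stinging, erythema, erosions, and edema) or other causes" from 0 to 3 at every visit except Screening. The scored reactions become AEs only with medical intervention or withholding. For the rest: "Any LSRs that are not listed above will be recorded as AEs".
- Section 8.4.7: LSRs associated with retinoids "should not be reported as AEs unless the LSRs required medical intervention or withholding application of study medication". It does not separate scored from unscored reactions, but it refers the reader to 8.3.3 for the full rule.

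Section 2.3 lists the local reactions expected of a retinoid: "burning, dryness, edema, erythema, hyperpigmentation, hypopigmentation, photosensitivity, pruritus, scaling/peeling, stinging, and tenderness". Pruritus is on that list but is not one of the four scored items.

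Two other places matter. The synopsis names persistent pruritus of Grade 2 or above among its examples of reasons to interrupt treatment, whereas Section 7.4 speaks of a persistent Grade 2 or greater adverse event. The I-NRS, which 8.2.3 describes as rating "the worst level of itching due to CI in the past 24 hours", is scheduled at Visits 2, 5 and 6 only.

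**The concern.** A site that sees itch at Visit 5 or 6 can find one answer in 8.2.3 and another in 8.3.3. Pruritus AE counts may then depend on which section the site follows. The most awkward case is itch that caused study medication to be withheld but was not treated: 8.2.3 as written leaves it out of the AE record.

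The itch scores do not fully make up for this. No pruritus item is named on the LSR form, and no I-NRS is taken at Week 2 or Week 4, although Section 7.4 expects irritation especially early in treatment. The 0-3 LSR scale does not cover pruritus and the I-NRS runs from 0 to 10, so a Grade 2 itch trigger has no scheduled measurement behind it.

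The stake is the tolerability comparison between two concentrations. Section 9.2 says the study is meant to assist dose selection for Phase 3, and Section 2.3 reports itchy erythema in responders to an earlier topical isotretinoin cream.

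**Working it through.** The plan states no figure on this point, so there is none to reproduce. The check applies each rule to pruritus found with the I-NRS, for the four combinations of therapy and withholding.

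| Therapy | Withholding | AE under 8.2.3 | AE under 8.3.3 (unlisted LSR) | AE under 8.4.7 read alone |
|---|---|---|---|---|
| No | No | No | Yes | No |
| No | Yes | No | Yes | Yes |
| Yes | No | Yes | Yes | Yes |
| Yes | Yes | Yes | Yes | Yes |

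The rules disagree in 2 of 4 rows. In the second row 8.2.3 stands alone against the other two sections, and the synopsis foresees that row. The third row takes therapy in 8.2.3 to mean the same as medical intervention in 8.4.7. Section 8.3.3 gives prescription medication as its example of intervention, while Section 6.5 allows over-the-counter low-potency hydrocortisone and bland emollients in some cases, so the status of such treatment under 8.4.7 is unclear.

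For other unlisted reactions, such as dryness or peeling, 8.2.3 is silent. Sections 8.3.3 and 8.4.7 differ only where there is neither intervention nor withholding, and the cross-reference in 8.4.7 points to 8.3.3.

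**Collection by visit (Schedule of Activities).** Weeks 2 and 4 (Visits 3 and 4): LSR form yes, I-NRS no. Weeks 8 and 12 (Visits 5 and 6): both. Hence there is no scheduled itch score at Weeks 2 and 4. An itch recorded as an AE would carry a mild, moderate or severe rating under Appendix 4, but only if it is recorded as one. Where the I-NRS is taken, it does not isolate drug-related itch: 8.2.3 frames it as itch from the disease, and the form in Appendix 11 assigns no cause.

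**Scale.** With 15 subjects per arm (Section 9.2), one subject is 1/15 = 6.7%. Section 9.4.2 calls a TEAE common at 5% or more, and 0.05 × 15 = 0.75 of a subject. One recording decision can therefore move pruritus on or off that summary.

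**Illustration with assumed values.** The documents give neither the incidence of itch nor the fraction recorded. If the true incidence is t and a fraction r is recorded, the chance that an arm of 15 shows no case is (1 − t·r)^15.

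| True incidence t | All recorded | Half recorded | A quarter recorded |
|---|---|---|---|
| 10% | 21% | 46% | 68% |
| 20% | 3.5% | 21% | 46% |
| 40% | <0.1% | 3.5% | 21% |

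For example, at t = 20% and r = 0.5: (1 − 0.10)^15 = 0.206.

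**The case against.** The strongest reply is that the documents mostly resolve themselves. Section 8.4.7 defers to 8.3.3, and 8.3.3 makes unlisted reactions AEs. Section 8.2.3 reaches only itch found with the I-NRS, so it has no force at Weeks 2 and 4. Itch reported then falls under 8.3.3 and the general instruction in 8.4 to record all AEs, with open-ended questioning under 8.4.2. All of this stands. It reduces the issue for reactions other than pruritus to a clarification, and it means that early itch is without a scheduled score, not without any route into the record. It does not settle pruritus at Visits 5 and 6, because 8.2.3 contains no pointer to 8.3.3.

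A reader might infer more than the text supports:

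- *That the main local harms go uncounted.* Burning/stinging, erythema, erosions and edema are scored and tabulated whatever their AE status (Protocol 9.4.3.5, SAP 8.2), and 9.4.3.5 also mentions other reactions.
- *That seven of the eleven terms in Section 2.3 are lost because only four are on the form.* That count does not measure harm. Dryness and scaling overlap with the disease, scaling is graded by VIIS and IGA at every visit, and the cross-reference sends unlisted reactions to the AE record.
- *That the loss falls mostly on the active arms.* Section 7.4 says the vehicle may also cause reactions.
- *That sites will report differently.* The text supports only that they may.

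**Conclusion.** The conflict is real and is confined to pruritus. Section 8.2.3 contradicts 8.3.3 when itch is not treated, and contradicts both 8.3.3 and 8.4.7 when itch led only to withholding. Separately, the synopsis relies on a pruritus grade for which no 0-3 score is collected at any visit, and no itch score of any kind is scheduled at Weeks 2 and 4.

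Each affected subject is worth 6.7 percentage points of an arm's incidence. How many would be affected cannot be derived from the documents; the probabilities above rest on assumed incidences and recording fractions. The point concerns recording and tabulation of tolerability. It does not touch the primary endpoint. It should be fixed because the change is cheap and the study is to inform dose selection.

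**What to change.** 1. Reconcile Sections 8.2.3, 8.3.3 and 8.4.7 into one AE-recording rule for pruritus that counts withholding of study medication as well as therapy, and say whether over-the-counter treatment counts as therapy.
2. Add pruritus to the existing 0-3 LSR form at Baseline and every post-Baseline visit. Tabulate it with the other LSRs whatever its AE status, and add it to the LSR summary in SAP 8.2 and Table 14.3.6.1.
3. State which AE rule applies to pruritus once it is listed. Without this the change works against itself, because 8.3.3 exempts listed LSRs from AE recording unless there is intervention or withholding.
4. State in 8.4.7 that its exemption covers only the scored LSRs, as its cross-reference to 8.3.3 already implies.
5. Reconcile the synopsis and Section 7.4 on the grade and type of event to which the interruption scheme refers. Which clinical rule is right is for the sponsor to decide.

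The cost is some protocol and SAP wording, one form row and somewhat higher reported counts. No visit is added.
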